Severe:

The event interferes considerable with the subject's usual activities. The event is of definite concern to the subject and/or poses substantial risk to the subject's health or well-being. The event is likely to require medical intervention and/or close follow-up and may be incapacitating or life threatening. Hospitalization and treatment may be required.

NOTE: The term "severe" refers to the intensity of the event and can be used with any event, without regard to whether or not it meets the criteria for being classified as "serious" or "unanticipated". For example, a subject can have a severe headache, but it is not a serious event.

3. Outcome Definitions

The outcome is in relationship to the Adverse Event, not the treatment rendered for the event (if any).

Resolved:

The adverse event has been resolved and/or no further treatment is required to treat the reported condition or illness.

Tolerated:

The adverse event will most likely never be resolved. The subject “tolerates” the illness or condition as a matter of life.

Pending:

Treatment or diagnostic studies were prescribed for the adverse event and the outcome of the adverse event is not yet known.

Study Withdrawal:

Due to the adverse event, the subject was withdrawn from the study.

Device Removal:

The adverse event resulted in reoperation and removal of a study device.

Reoperation of Affected Hip:

The adverse event resulted in reoperation of the fracture, but the reoperation did not include removal of a study device.

Death:

The outcome indicates the subject died as a direct result of the reported adverse event.

F. Monitoring of the Study

Prior to initiating the clinical study, the Sponsor may conduct a site evaluation visit to ensure the Investigator(s) and study staff understands the study protocol and requirements and have adequate time and resources to implement and conduct the study. Prior to study initiation, the Investigator must have a fully executed CTA and IRB or EC approval of the study protocol and the study Informed Consent.

During the course of the study, the Sponsor will conduct periodic central monitoring and maintain contact with the study staff to monitor compliance and evidence of adverse events, in accordance with the Sponsor’s policies and procedures. The Sponsor will address any identified non-compliance with the executed CTA, study protocol, and applicable regulatory requirements.

If onsite monitoring visit(s) are deemed appropriate by the Sponsor, the Investigator will permit representatives of the Sponsor’s monitoring team to have direct access to inspect all source data/documents, study

documents/binders, study subject case report forms, corresponding sections of study subject medical/hospital records, and any other documents relevant to the study. All Sponsor visits (including site initiation) will be documented using the **Site Monitoring Visit Log** (Appendix C).

X. Risk Analysis

This post-market clinical study is classified as minimal risk and there are no anticipated risks specific to study participation other than the potential loss of confidentiality. There are no experimental procedures in this study, and participation in this study is not anticipated to affect the medical treatment of enrolled subjects.

When used in accordance with product labeling, the risks associated with the use of N-Force Screws augmented with N-Force Blue are similar to those of standard intracapsular femur fracture treatment systems used for the same clinical indication or purpose. These risks are categorized below as either general surgical risks or risks associated with the intracapsular femur fracture procedure/study device. Unanticipated adverse events can also occur.

For general surgical risks, please refer to the FDA cleared instructions for use for this product.

XI. Statistical Considerations

Data collected in this study will be summarized descriptively and descriptive summaries will be the basis of any study reports issued. These summaries may be used for interim study reports and may also be used to support regulatory submissions, presentations, and/or publications. Additional surgical technique and instrumentation data may be collected and evaluated.

A. General Statistical Methods

Statistical methodology will consist of summarizing collected data descriptively. Categorical data (e.g., gender or race) will be summarized using counts and percentages, and 95% Confidence Interval (CI), over the time periods of interest. Continuous data, such as age, will be summarized by using means, medians, standard deviation, minimum, maximum, and 95% CI over the time periods of interest.

B. Sample Size

Using an observed historical control performance reoperation rate of ~15% ^{[4][7]},

for intracapsular femur fractures, 151 evaluable subjects will be required at 12 months follow-up to show necessary statistical improvement from the historical revision rate. With an expected lost to follow-up rate of 20%, 190 subjects will be required for this clinical study. The assumed reoperation rate for the N-Force Screws augmented with N-Force Blue is 7.5%.

XII. Quality Control & Quality Assurance

The study is conducted in accordance with the Declaration of Helsinki and the ISO 14155:2011.

The Investigator will be required to permit representative(s) of the Sponsor's monitoring team to inspect all Case Report Forms and corresponding sections of the study patients office records and/or hospital original medical records. These audits will be done for quality assurance purposes, i.e. verifying adherence to the Clinical Investigation Plan and the completeness and accuracy of the data being entered on the Case Report Forms.

The Clinical Investigation Plan will be provided to all participating study centers. The Investigators will be fully trained in the proper reporting and submission of trial data prior to patient enrolment. Completed Case Report Forms will be reviewed before entering the data into a central database by the Sponsor.

The Clinical Study Manager is responsible for generating data queries for missing or unclear data if needed. It is the responsibility of the Clinical Study Manager to ensure data quality.

There are regular meetings between the Investigators and Zimmer Biomet Clinical Affairs staff. Written correspondence to all sites is used to inform the Investigators of routine study details and to update them on study status.

XIII. Suspension or Premature Termination of the Clinical Investigation¹

Sponsor may suspend or prematurely terminate clinical investigation site(s) or entire clinical investigation for significant and documented reasons. If suspension or premature termination occurs at an individual investigation site, sponsor shall inform the responsible regulatory authority(s) as appropriate and ensure that ethic committee(s) are notified. If the suspension or premature termination was in the interest of safety, the sponsor shall inform all other principal investigators. If suspension or premature termination occurs,

- The sponsor shall remain responsible for providing resources to fulfill the obligations from the clinical investigation plan and existing agreements for following up the subjects enrolled in the clinical investigation, and

- The principal investigator or authorized designee shall promptly inform the enrolled subjects at his/her investigation site, if appropriate.

XIV. Amendments to the Clinical Investigation Plan

All amendments shall be agreed upon with the Sponsor and the Investigator and be recorded with a justification for the amendment. Approval of the Institutional Review Board that reviewed the original protocol must be obtained if required according to the corresponding regulations. In the case of an amendment to the protocol, the revision history shall be documented.

XV. Publication Policy

Both the Clinical Investigator and the Sponsor have the right to publish or allow the results of the clinical trial to be published. The Clinical Investigator recognizes that the Sponsor has a special interest in the results of the clinical study and will submit manuscripts to the Sponsor prior to publication. If the Sponsor desires changes to be made, these are communicated to the Clinical Investigator within 30 days of submission. Pooled data may be used for training and meetings

XVI. Document History

Revision Number	Date	Description of Change	Person in Charge of Change
2.0	18JUN2018	Inclusion/Exclusion Criteria Updated	[name]
3.0	20JAN2020	Inclusion Criteria Updated; AE Definitions Updated; Section 12, 13, 14, 15, and 16 added.	[name]

References

- [1] ISO 14155:2011(E). International Standard for Clinical investigation of medical devices for human subjects – Good clinical practice
- [2] Code of Federal Regulations
 - Code of Federal Regulations, Title 21, Part 11: Electronic Records; Electronic Signatures
 - Code of Federal Regulations, Title 21, Part 50: Protection of Human Subjects
 - Code of Federal Regulations, Title 21, Part 56: Institutional Review Boards
- [3] <https://www.aaos.org/research/guidelines/hipfxguideline.pdf>
- [4] Bhandari M et al. Fracture fixation in the operative management of hip fractures (FAITH): an international, multicentre, randomised controlled trial. Lancet. 2017; 389(10078):1519-1527. DOI:10.1016/S0140-6736(17)30066-1.
- [5] Russell TA, The Problem of Fracture Fixation Augmentation and Description of a Novel Technique and Implant for Femoral Neck Stabilization, Techniques in Orthopaedics Vol. 30 Nr. 1 2015

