	
 • Patient receives operative treatment within 7 days of injury. • Patient was ambulatory before injury. • Patient is 50 years of age or older. 
Exclusion Criteria:
 
 • Patient has Garden III or IV intracapsular proximal femur fracture. • Patient has major cognitive impairment (including dementia). • Patient is on dialysis. • Patient is not expected to survive follow-up schedule. • Patient is expected to have problems maintaining follow-up compliance, i.e. patients with no fixed address, patients not mentally competent to give informed consent, etc. (Investigator's discretion). • Patient is a prisoner. • Patient is known to be pregnant and/or breastfeeding. • Patient is a known alcohol or drug abuser. • Patient had previous/has active acute or chronic infections, especially at the site of operation. • Patient has non-viable bone, or has areas where surrounding bone is not viable or capable of supporting and anchoring the implant. • Patient has traumatic injuries with open wounds or close to the proximal femur fracture, which are likely to become infected. • Patient is expected to be non-compliant with recommended post-operative weight-bearing instructions. • Physical conditions, in the opinion of the investigator, that would prohibit adequate implant support or impede healing.
Study Device	N-Force Fixation System 7.3 mm (Non-fenestrated/fenestrated) applied with washers; N-Force Blue (Bone Substitute Material)
Outcome Measures	
 • RUSH Score • FIX-IT • Avascular necrosis (Steinberg classification) rate at 12 months follow-up • Harris Hip Score • Timed "Up-And-Go" Test • EQ-5D-5L • Adverse Events

Documentation	Electronic Case Report Forms
Statistical Reporting	Data collected will be summarized and reported to each participating investigator. Statistical analysis will be conducted by Zimmer Biomet or its designee.

This protocol is compliant with ISO 14155 Standard for Clinical Investigation of Medical Devices For Human Subjects – Good Clinical Practice ^[1] , is in accordance with US Code of Federal Regulations 21 CFR Parts 11, 50 and 56 ² , and The Declaration of Helsinki (DoH) – Ethical principles for medical research involving human subjects.

II. Data Collection Overview

The following table indicates the necessary case report forms to be completed at the given time point:

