4. Adverse Event Report(s) (as applicable)
5. Protocol Deviation(s) (as applicable)
6. Implanted Device Form (as applicable)
7. Study Completion (as applicable)

J. Post-surgical management

Post-surgical management for study subjects will follow the investigator's standard of care for patients undergoing intracapsular proximal femur fracture. Post-surgical rehabilitative therapy will be as prescribed by the investigator.

K. Post-operative Follow-up Procedures (Data Collection)

Post-operative clinical evaluations/assessments will be conducted at 6 weeks \pm 14 days, 3 months \pm 30 days, 6 months \pm 60 days, and 12 months \pm 90 days post-surgery. The following case report forms will be collected at each interval:

1. Postoperative Follow-up
2. X-rays (AP and Lateral)
3. Physician Radiograph Assessment including RUSH

4. Steinberg Classification (12 months Follow-Up only)

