5. EQ-5D-5L
6. FIX-IT
7. Timed “Up and Go” Test
8. Harris Hip Score
9. Adverse Event Reports(s) (as applicable)
10. Protocol Deviation(s) (as applicable)
11. Implanted Device Form (as applicable)
12. Study Completion (as applicable)

Subjects will be followed post-operatively for 12 months. Unless the study is otherwise closed, data will continue to be collected until the subject completes the study per the protocol, voluntarily withdraws from the study, is withdrawn from the study by the investigator, is lost to follow-up, undergoes revision to remove a study device (due to complication), or expires. See Management of Incurrent Events (Section IX, Subsection D of this protocol) for additional details. Reason(s) for study completion must be documented on the Study Completion case report form.

L. Minimization of Subjects Lost to Follow-up

Subject follow-up is extremely important for the conduct of a clinical study, and the expectation is to maintain the highest possible rate of follow-up compliance throughout this study. During the informed consent process and at each follow-up interval, subjects should be counseled on the importance of completing future study follow-up intervals.

M. Radiographic Definitions and Methods

All postoperative radiographic evaluations performed according to the protocol will be reviewed by the Investigator at the time of the evaluation and documented using the **Physician Assessment of Post-op Radiographs** case report form. This includes documentation of any significant radiographic findings. In addition, an **Adverse Event** case report form must be completed for those findings indicated by an asterisk on the **Physicians Assessment of Post-op Radiograph** case report form, or for any other findings identified as an adverse event.

[figure not shown]
o **Method to derive the length of the femoral neck:**

1. Draw a line along the femoral shaft axis.
2. Draw a line along the femoral neck axis.
3. Measure the distance CD (blue line) in millimeter.
4. Measure the distance AB (red line) of the **inferior** screw in millimeter.

[figure not shown]
To adjust for x-ray magnification the actual length of the femoral neck will be calculated using the following formula:

$$\text{Length of the femoral neck [mm]} = CD_{\text{measured}} \times \frac{AB_{\text{true}}}{AB_{\text{measured}}}$$

$$AB_{\text{true}} = \text{Known screw length [mm]}.$$

[figure not shown]

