- **Non-union definition:** A total RUSH score below 18 at six month post-surgery is considered a non-union [9].
 - RUSH scoring examples:

	Cortical Bridging	Cortical Fracture Line Disappearance
Anterior	1	2
Posterior	1	1
Medial	1	1
Lateral	1	1
Total:	4	5

Trabecular Consolidation	1
Trabecular Fracture Line Disappearance	1
RUSH Total:	11

	Cortical Bridging	Cortical Fracture Line Disappearance
Anterior	3	3
Posterior	2	2
Medial	2	2
Lateral	3	3
Total:	10	10

Trabecular Consolidation	3
Trabecular Fracture Line Disappearance	3
RUSH Total:	26

1. Required radiographic views

Standing anteroposterior (AP) (a supine AP view will be accepted if the patient is unable to stand), and standard lateral radiographs of the operative femur are required to be captured at the pre-op, operative/post-op, 6 weeks, 3 months, 6 months, and 12 months post-surgery.

Radiographs should have similar exposure and must show the entire study device and surrounding bone. For consistency, every effort should be made to capture all radiographic views for a given subject using the same institution throughout the study. However, radiographs captured at a different institution may be used for the study, provided they meet required study specifications and are captured within the required interval window. The investigative site will retain copies (hard copy/CD/digital) of all radiographs referenced for the study.

2. Submission to Sponsor

At the Sponsor's discretion, study radiographs may be requested from the sites for independent radiographic review and assessment of appropriate parameters.

N. Recommended Revision Procedure

See Management of Incurrent Events (Section IX, Subsection D of this protocol)

IX. Reporting

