In the event that removal of one or more of the study related components is necessary (due to complication), the Investigator will determine the best treatment and/or revision method for the subject.

Prior to revision surgery, the Investigator or qualified Designee must document any significant radiographic findings related to the need for revision on the **Physician Assessment of Postop Radiographs** case report form. An **Adverse Event** case report form must be completed for those findings indicated by an asterisk on the **Physicians Assessment of Postop Radiograph** case report form.

Once the revision surgery has been completed, the Investigator or qualified Designee must complete an **Adverse Event Report** case report form as well as a **Study Completion** case report form terminating the subject from the study. For the study completion status, select “Study Device Removed”. This procedure also applies to partial revisions e.g. removal of one of the three screws.

4. Investigator Withdrawal

The Investigator can choose to withdraw a subject from the study if the subject no longer meets study inclusion/exclusion criteria. The reason for the Investigator’s withdrawal of the subject must be documented on the **Study Completion** case report form.

5. Subject Withdrawal

Study subjects may choose to withdraw from the study at any time, for any reason. If possible, a final evaluation will be completed for any subject who no longer wishes to participate in the study. The reason for the subject withdrawal must be documented on the **Study Completion** case report form.

6. Lost to Follow-up

A study subject will be considered lost to follow-up after they have missed a visit and a reasonable number of attempts to locate and evaluate them have failed. All attempts to contact the subject are to be documented in the subject's medical record and on the **Study Completion** case report form. In particular, the reason for the Study Completion must be documented. Missed visit(s) also must be documented using the **Protocol Deviation** case report form, unless the visit is retrospective.

7. Protocol Deviations

Investigators should not deviate from the study protocol. If a protocol deviation does occur, the deviation must be documented on the **Protocol Deviation** case report form and submitted to the Sponsor. If applicable per their reporting requirements, the Investigator or Designee will also report applicable protocol deviations to their IRB or EC.

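### Follow-up ends when a study component is removed for a complication and no rule covers removed subjects, so by default the later union and avascular necrosis rates describe only subjects whose device stayed in

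*Combined protocol and SAP*

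**What the plan says.** **When follow-up stops.** Section VIII.K says that "data will continue to be collected until the subject completes the study per the protocol", unless one of several events comes first; the list ends with a subject who "undergoes revision to remove a study device (due to complication), or expires". Section IX.D.8 repeats this. Section IX.D.3 puts it into practice with a Study Completion "case report form terminating the subject from the study", and adds: "This procedure also applies to partial revisions e.g. removal of one of the three screws".

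**What is recorded at revision.** Section IX.D.3 requires the investigator to "document any significant radiographic findings related to the need for revision". In the schedule in section II, the Revision column requires X-rays, the adverse event form and the completion form. The radiographic assessment with RUSH is marked as applicable. Steinberg, FIX-IT, Harris Hip Score, Timed Up and Go and EQ-5D-5L have no entry there.

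**What is to be reported.** Section IV defines Performance as the union rate at 6 weeks and 3, 6 and 12 months. The synopsis lists "Avascular necrosis (Steinberg classification) rate at 12 months follow-up", and sections II and VIII.K schedule the Steinberg grading at the 12-month visit alone. Section VIII.M gives the only healing cut-off: "A total RUSH score below 18 at six month post-surgery is considered a non-union".

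**How it is analysed.** Section XI.A provides descriptive summaries of the collected data. It names no analysis set or denominator for these rates and gives no rule for subjects whose device was removed.

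**The concern.** A removal for a complication is often the very failure that the union and AVN outcomes are meant to show. Under these collection rules, the subject leaves the data at that moment. Someone whose screws come out at month 4 because the fracture has not healed has no 6-month RUSH score and cannot meet the non-union definition. Someone revised at month 8 for AVN never receives a Steinberg grade. If section XI is followed as written, both are absent from the later rates and are not counted as failures.

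At stake is the plan's own Performance measure and its 12-month AVN rate. Section IV also announces a comparison with a historic control. Without a stated denominator, a reader cannot tell whether the two sets of rates cover the same kind of subject.

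**Working it through.** **The plan's own figure.** Section XI.B gives p0 = 15% (historical), p1 = 7.5% (assumed for the device) and n = 151. It states neither alpha nor power; I assume two-sided 0.05 and 80%. With n = [(z_α√(p0(1−p0)) + z_β√(p1(1−p1)))/(p0−p1)]²:

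[(1.960×0.3571 + 0.8416×0.2634)/0.075]² = 150.97, so 151.

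Allowing for 20% loss, 151/0.8 = 188.75, close to the stated 190. The sample size reproduces and is not affected by this point.

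**How many subjects.** 151×0.075 = 11.3 and 151×0.15 = 22.7 reoperations. These only approximate the number of removals. Some reoperations remove nothing, while a complication-driven removal after healing also ends follow-up and may not be a listed reoperation. The 15% is the historical rate, not the rate assumed for this device.

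**Union at 12 months (illustration).** The documents give no union rate, removal timing or healed share. Let U be union in retained subjects, q the share removed and h the share of removed subjects already healed at removal. Removal before union counts as failure.

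Composite success = U(1−q) + qh; overstatement by the device-in-place rate = q(U−h).

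| Assumed U = 95% | h = 0 | h = 0.5 | h = 1 |
|---|---|---|---|
| q = 7.5% | 87.9% | 91.6% | 95.4% |
| q = 15% | 80.8% | 88.3% | 95.8% |

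- At q = 7.5% the largest overstatement is 0.075×0.95 = 7.1 points.
- For U from 90% to 98% at q = 7.5%, it is 6.8 to 7.4 points (h = 0) or 3.0 to 3.6 points (h = 0.5). With h = 1 it becomes an understatement of 0.2 to 0.8 points.
- It is zero when h = U.

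The h = 0 figures are lower bounds on union itself, because a subject could still unite after a partial removal or refixation.

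**AVN at 12 months (illustration).** Let A be the rate in retained subjects and a the share of removed subjects with AVN at revision. Rate = A(1−q) + qa, with q = 7.5%:

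| Assumed A | a = 0 | a = 25% | a = 50% |
|---|---|---|---|
| 2% | 1.9% | 3.7% | 5.6% |
| 5% | 4.6% | 6.5% | 8.4% |
| 10% | 9.3% | 11.1% | 13.0% |

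The device-in-place rate is too low when a exceeds A and slightly too high when a is below A.

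**Timing.** If removals were spread evenly over the year (an assumption), half of the 11.3, about 6, would fall before month 6 and escape the non-union definition. Subjects removed after the 6-month visit would already have that RUSH score.

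**The case against.** The strongest reply is that the information is not lost. X-rays are required at revision, the findings behind the revision must be documented, RUSH can be scored, and adverse events are a secondary endpoint. Healing status at removal may well be recoverable, and AVN may appear as an adverse event. The case report forms are not among the documents reviewed, so the findings they flag cannot be judged. All of this stands. But no Steinberg grade is scheduled at revision, and no stated rule carries any of this information into the union or AVN rate.

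A second reply is that the plan nowhere says removed subjects are excluded. That is correct: a reader might infer a declared device-in-place analysis set, and the documents contain none. The restriction is the default result of when data are collected. A sponsor could still count removals as failures, but that choice should be fixed before the data are seen.

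A reader might also infer that the primary endpoint is biased. The documents do not support this. Removal before healing, refixation and conversion to total hip arthroplasty are listed events in section IV, recorded as the subject leaves. Reoperations that remove nothing do not trigger the exit rule, as sections VIII.K and IX.D.8 imply. One small gap remains: a removal after healing may not be a listed event, and a later reoperation in that subject would go unrecorded.

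Finally, it is tempting to extend the point to cost-effectiveness and function. The schedule names no resource-use form for any subject, so the cost gap is mostly not caused by removals; what removal adds is the loss of later EQ-5D-5L. A favourable direction for function scores is plausible, but the documents do not show it.

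**Conclusion.** The point holds for the union and AVN rates and should be fixed. It follows from stated collection rules combined with the absence of a rule for removed subjects, so it is more than missing detail.

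The gap is certain; its size is not. At 7.5% removed and an assumed 95% union in retained subjects, the overstatement of union is at most about 7 points, and it vanishes or slightly reverses if nearly all removed subjects had healed. An assumed 5% AVN would become 4.6% to 8.4% if 0% to 50% of removed subjects had AVN. A reader might take 87.9% as the true 12-month union rate. It is a composite that counts removal before union as failure, and it rests on assumed inputs.

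The primary endpoint is largely unaffected, and the sample size is untouched.

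**What to change.** 1. **Schedule (section II).** Add a Steinberg reading to the Revision column and make the RUSH reading there required, both from the X-rays already required at revision.

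2. **Section XI.** Report one composite at each visit, over all implanted subjects:
   - Success is documented union with no earlier removal before documented union.
   - Any complication-driven removal before documented union is a failure, whatever its reason.
   - Subjects removed after documented union count as united and are also listed separately.
   - Loss to follow-up is shown separately.

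   State the union criterion applied at each visit. The composite needs it, and the plan gives only a 6-month non-union cut-off. Count AVN documented at or before revision as AVN in the 12-month rate. Give the device-in-place rates as supplementary results.

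Continued data collection after removal is optional and not part of the core fix. It would involve roughly 14 to 29 of 190 subjects (190×0.075 = 14.25; 190×0.15 = 28.5). Without it, AVN that arises after removal stays unseen.

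**Cost.** A protocol amendment, with ethics approval where required (sections IX.D.9 and XIV), a small case report form change, and somewhat less favourable secondary rates. The core fix adds no visit and no imaging.
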